3.5.2 Exclusion Criteria

- Persons with a known positive SARS-CoV-2 test > 28 days ago.

Those who are negative for SARS-CoV-2 at enrolment will not be followed further in the observational cohort. If the test result is indeterminate, re-testing may be carried out according to local standards.

Individuals who have previously been tested

Individuals with a previous positive test for SARS-CoV-2 within 3 days of enrollment may be enrolled without the need for a repeat test at enrollment. If the positive test was > 3 days and < 28 days before enrollment the test will need to be repeated at enrollment.

[figure not shown]
3.5.3 Study Sites

This study will be conducted in geographic locations where the incidence of COVID-19 is high. To avoid enrolling a large number of individuals testing negative to SARS-CoV-2, participation of sites that are registered to conduct this study may be paused depending on the prevalence of positive test results for SARS-CoV-2 in their area.

Since the handling of clinical specimens may be problematic at many testing locations, the collection of study specimens will be limited to a substudy involving selected sites (see Appendix F).

3.6 Study Plan

The study plan is depicted in Figure 1.

Figure 1: Study plan for participants undergoing SARS-CoV-2 testing and consenting to participation in this observational study.

Footnote

*on the day of enrolment or test done within 3 days before enrolment

¥ includes COVID-19 related out-patient treatments

Enrolment

Outpatient testing for SARS-CoV-2 may be performed in a variety of ways and for a variety of reasons. To avoid risk to health care workers, in many locations, special facilities are being identified for rapid identification of those with COVID-19. We refer to these as “testing stations”. Since the testing stations are likely to be overwhelmed with people seeking testing, we anticipate that separate areas will have to be identified to consent participants for this research study and to collect the required data. We refer to these as “research stations”. Collaborations between the testing and research stations will be important.

For participants who consent to the study, permission to release medical records will be sought and reasons for hospitalization and events during hospitalization will be requested. Information regarding demographics; medical history, including co-morbidities; onset date of symptoms; targeted symptoms, including difficulty breathing; smoking; and targeted medications will be obtained. Contact information for one or two persons who know(s) the participant’s whereabouts will also be recorded.

At the time of enrolment, selected sites participating in a substudy (see Appendix F) will be asked to obtain separate consent for the swabs from the upper respiratory tract and a blood sample sufficient for 4mL of serum to be shipped to a central repository for future respiratory virus research; and 2) co-enrolment in the INSIGHT Genomics Study (INSIGHT 004) where a blood sample sufficient for obtaining 6mL whole blood will be collected and stored. These specimens will be sent to a central repository in the United States for storage.

Proposed research utilizing stored specimens collected per this protocol will be reviewed and approved by the Protocol Team, the INSIGHT Scientific Steering Committee, and NIAID.

Disclosure of SARS-CoV-2 Test Result

Participants already known SARS-CoV-2 positive within 28 days of enrollment are eligible. If the documented positive test was within 3 days of enrolment they do not need to be retested at enrolment, and will be followed for 28 days. For others being tested at enrolment, results may not be available on the day of enrolment. When the test results become available, participants will be contacted with the test result. If positive for SARS-CoV-2, these participants will be followed for 28 days.

Participants who do not have a positive test result for SARS-CoV-2 at enrolment will not be followed. Repeat testing can be carried out following local guidelines.

Follow-up of SARS-CoV-2 positive participants

During the follow-up period, the status of each participant will be assessed at 7, 14 and 28 days following enrolment. Status may be checked by telephone or by means other than face-to-face visits (e.g., text messages).

Follow-up assessments at 7, 14 and 28 days will include:

- Vital status
- Hospitalization status
- Specific symptoms, including difficulty breathing
- General health status
- COVID-19 related out-patient treatments
- Targeted medications

Participants hospitalized during the 28 day follow-up period may be invited to participate in FLU 003 Plus, if the location of their hospitalization is a FLU 003 Plus site.

[figure not shown]
In summary, there are 4 time points at which data are collected for this observational study:

- 1) enrolment (in person),
- 2) at day 7 (may be by telephone or other means),
- 3) at day 14 (may be by telephone or other means) and
- 4) at day 28 (may be by telephone or other means).

Follow-up will continue through day 28 for all participants regardless of enrolment in other studies or hospitalization prior to day 28.

Figure 2 illustrates how information from the observational cohort study could be used to identify participants for an INSIGHT clinical trial or for FLU 003 Plus.

Figure 2: Study plan for participants in this observational study who may co-enrol in other protocols. Note: participants in this observational study with SARS-CoV-2 infection will be followed for 28 days regardless of participation in other protocols.

3.7 Study Withdrawal

Participants may withdraw from this observational study at any time at their request.

4 Evaluation

4.1 Data Analysis

Simple descriptive statistics will be used to describe all participants enrolled, as well as those with and without a positive test for SARS-CoV-2. Participant characteristics at enrolment will be summarized by geographic region, and by calendar time within geographic region. Participant characteristics will be compared for those with and without a positive test for SARS-CoV-2.

Symptoms, including severity of dyspnoea, will be summarized, and determinates of a positive test will be identified using logistic regression models. Factors other than symptoms include, for example, age, sex, co-morbidities, and time since onset of symptoms.

For participants who tested positive for SARS-CoV-2, follow-up data will be collected at days 7, 14, and 28. Disease severity at each time point will be summarized in an ordinal outcome that considers death, hospitalization, and general health status.

Risk factors for the outcomes (e.g., hospitalization, worsening of general health status) at 7, 14, and 28 days after enrolment will be examined using logistic regression models. Reasons for hospitalization will also be considered and analyses for specific reasons for hospitalization will be pursued. Risk factors will include demographic factors (e.g., age, sex, geographical region), clinical factors (e.g., co-morbidities, smoking status), symptoms and severity of dyspnoea at enrolment, and calendar time (to assess the influence of season, or a change in disease severity in the study population over time).

In addition to describing disease status at fixed time points, Kaplan-Meier estimates will be used to describe time to the composite outcome of hospitalization or death, overall and within subgroups. Factors associated with time to hospitalization or death will be investigated using Cox proportional hazards models.

All statistical models will be stratified by geographic region, unless the event numbers are too low. We will consider other stratifying models that include stratification by geographic region and calendar time if event numbers are sufficient.

As new data on COVID-19 become available, from this and other studies, data collection and analysis may change to address emerging research questions. Further details on the proposed data analysis will be provided in a Statistical Analysis Plan.

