1. Compare characteristics, including demographics, co-morbid conditions or immunosuppression, and other risk factors for disease progression, including hospitalization or death, for the global cohort and by geographic region between those who have a positive test for the SARS-CoV-2 virus versus those who have a negative test.
2. Among those positive for SARS-CoV-2:
 - a. Evaluate health status and the percentage reporting excellent or very good health status during follow-up.
 - b. Determine the percentage reporting a return to pre-morbid health status during follow-up.
 - c. Evaluate change in severity of dyspnoea using a standardized questionnaire during follow-up.
3. In a substudy involving selected sites, establish a repository of baseline upper respiratory and blood samples for future studies. These studies will be aimed at molecular characterization of SARS-CoV-2, and the measurement of biomarkers that predict progression of disease. Among participants co-enrolling in INSIGHT 004: Genomics, DNA will be extracted for studies of host genetics to investigate the pathophysiology and host-viral interactions of COVID-19.
4. Use the data collected to inform the design of future randomized intervention studies aimed at reducing the rate of disease progression and morbidity.

Participant Selection

To be eligible for enrolment participants must be ≥ 18 years of age, not be hospitalized (outpatients), and have a signed informed consent. Participants with SARS-CoV-2 infection will be followed for 28 days from enrolment.

Study Plan

Participants who consent for the study and have SARS-CoV-2 infection/COVID-19, will be followed for 28 days in an observational cohort study.

Procedures and data collection have been streamlined to facilitate the enrolment of a large number of adults at INSIGHT sites around the world.

The general aim of this study is to identify risk factors for disease progression, e.g., hospitalization or death. This information will be used to plan and rapidly enrol randomized trials of treatments for COVID-19. Protocols which are developed for the randomized trials by INSIGHT will be separate from this protocol.

2 Background and Rationale

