3.2 Study Objectives

The two primary objectives of this observational study are:

Among those who are positive for SARS-CoV-2:

1. Estimate the rate of hospitalization or death during the 28 day follow-up period.
2. Identify risk factors for hospitalization or death.

Other objectives are:

1. Compare characteristics, including demographics, co-morbid conditions or immunosuppression, and other risk factors for disease progression, including hospitalization or death, for the global cohort and by geographic region between those who test positive for the SARS-CoV-2 virus versus those who test negative.
2. Among those who are positive for SARS-CoV-2
 - a. Evaluate health status and the percentage reporting excellent or very good health status during follow-up.
 - b. Determine the percentage reporting a return to pre-morbid health status during follow-up.
 - c. Evaluate change in severity of dyspnoea using a standardized questionnaire²² during follow-up.
3. In a substudy involving selected sites, establish a repository of baseline upper respiratory and blood samples for future studies. These studies will be aimed at molecular characterization of SARS-CoV-2, and the measurement of biomarkers that predict progression of disease. Among participants co-enrolling in INSIGHT 004: Genomics, DNA will be extracted for studies of host genetics to investigate the pathophysiology and host-viral interactions of COVID-19.
4. Use the data collected to inform the design of future randomized intervention studies aimed at reducing the rate of disease progression and morbidity.

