3.5 Participant Selection

This study intends to target enrolment at research sites that can recruit a large number of individuals with SARS-CoV-2. Thus, each participating site will be asked to describe the approach they plan to take for enrolling individuals. Sites may be asked to change their approach to enrolment if the expected percentage positive for SARS-CoV-2 is too low. Enrolment at registered sites may be paused if there are too few positive individuals being enrolled.

The inclusion and exclusion criteria for enrolment are given below.

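### The secondary comparison of positives and negatives, and the model for a positive test, take no account of entry as a known positive, so odds ratios for factors related to entry route can be distorted

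*Protocol*

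**What the plan says.** Section 4.1 first describes everyone enrolled and then says "Participant characteristics will be compared for those with and without a positive test for SARS-CoV-2". The next paragraph adds that "determinates of a positive test will be identified using logistic regression models", with symptoms, age, sex, co-morbidities and time since onset among the candidate factors. No narrower population is named. On adjustment it says "All statistical models will be stratified by geographic region, unless the event numbers are too low", and calendar time may be added; site and route of entry are not mentioned.

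The entry rules bring in two kinds of participant. Some are tested at enrolment with unknown status. Others are already known to be positive. Section 3.5.2 says "Individuals with a previous positive test for SARS-CoV-2 within 3 days of enrollment may be enrolled without the need for a repeat test"; those whose positive test is more than 3 and less than 28 days old are re-tested. Section 3.6 confirms both rules. Section 3.5 adds that "each participating site will be asked to describe the approach they plan to take for enrolling individuals" and that "Sites may be asked to change their approach to enrolment if the expected percentage positive for SARS-CoV-2 is too low".

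The groups are worded in more than one way. Other objective 1 compares, in the front summary, "between those who have a positive test for the SARS-CoV-2 virus versus those who have a negative test", and in section 3.2, "between those who test positive for the SARS-CoV-2 virus versus those who test negative". Sections 3.5.2 and 3.6 and footnote a of Appendix B decide who is followed by status at enrolment. The Figure 1 footnote accepts a test on the enrolment day or up to 3 days before.

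**The concern.** For someone enrolled on a positive result up to 3 days old, a positive test is the reason for entry, not an outcome that could have gone either way. Such a person can only be in the positive group. If the factor under study also differs by entry route, its odds ratio mixes what predicts a positive test with how people were recruited. Symptoms are the clearest example: they are recorded at enrolment, which for known positives can be days after the test.

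There is a second, smaller issue. A person with a documented positive more than 3 and less than 28 days earlier may re-test negative. The enrolment-status rule makes that person a negative. The summary objective and section 4.1 name no index test, so read literally the person fits both groups in the summary and the positive group in section 4.1.

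At stake are the odds ratios for other objective 1 and for the model of a positive test. Both primary objectives concern positives only.

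**Working it through.** The protocol gives no effect size, power or group shares for this comparison, so there is no stated figure to reproduce. Every input below is an assumption, chosen to show the range. Throughout, odds(p) = p/(1 − p).

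**1. Known positives pooled, factor related to the test result.** Assume a symptom in 60% of positives tested at enrolment and 40% of negatives. The odds ratio is odds(0.60)/odds(0.40) = 1.5/0.667 = 2.25. Let k be the share of the positive group who entered as known positives and s their symptom frequency. The pooled odds ratio is odds((1 − k) × 0.60 + k × s)/odds(0.40). For k = 25% and s = 30%, the mixed frequency is 0.525 and the odds ratio is 1.105/0.667 = 1.66.

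| s | k = 10% | 25% | 50% | 75% |
|---|---|---|---|---|
| 30% | 1.99 | 1.66 | 1.23 | 0.90 |
| 60% | 2.25 | 2.25 | 2.25 | 2.25 |
| 75% | 2.40 | 2.64 | 3.12 | 3.72 |

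The middle row is the key check: extra positives alone do not move an odds ratio.

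**2. Known positives pooled, factor unrelated to the test result.** Assume a fixed characteristic with 20% prevalence in everyone tested at enrolment, so the odds ratio there is 1. With prevalence q in known positives, the pooled value is odds((1 − k) × 0.20 + k × q)/odds(0.20).

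| q | k = 10% | 25% | 50% | 75% |
|---|---|---|---|---|
| 10% | 0.94 | 0.85 | 0.71 | 0.57 |
| 15% | 0.97 | 0.92 | 0.85 | 0.78 |
| 20% | 1.00 | 1.00 | 1.00 | 1.00 |
| 25% | 1.03 | 1.08 | 1.16 | 1.25 |
| 30% | 1.06 | 1.16 | 1.33 | 1.52 |

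**3. Earlier positives who re-test negative, counted as negatives.** Assume a true odds ratio of 2.0, from prevalences of 0.333 and 0.20, and that these people resemble the positives. If they are a share c of the negative group, its prevalence becomes (1 − c) × 0.20 + c × 0.333. For c = 1%, 2%, 5% and 10% the odds ratio is 1.98, 1.97, 1.92 and 1.84.

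**4. Precision of a restricted model.** With equal prevalence in all groups and r positives per negative, removing a share k of the positives multiplies the standard error of the log odds ratio by √[(1/(1 − k) + r)/(1 + r)].

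| r | k = 25% | 50% | 75% | 90% |
|---|---|---|---|---|
| 1 | 1.08 | 1.22 | 1.58 | 2.35 |
| 5 | 1.03 | 1.08 | 1.22 | 1.58 |

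If a share m of the negatives is removed as well, r in the numerator becomes r/(1 − m). For r = 1, k = 50% and m = 10% the factor is √[(2 + 1.111)/2] = 1.25 instead of 1.22.

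**The case against.** The strongest reply is that the choice of participants for a secondary model belongs in the statistical analysis plan, which section 4.1 promises and which is not at hand. That plan may well deal with it. But the protocol itself states the comparison and the model without restriction, while its entry rules admit people on the outcome being modelled.

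A reader might infer that the wordings flatly contradict each other. That goes too far. The follow-up rule consistently uses status at enrolment, the Figure 1 footnote gives a window, and the shorter phrases can be read as paraphrase. What stands is that this rule, carried into the comparison, places a documented recent case among the negatives. By step 3 the effect is small at small shares.

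A reader might also infer that the restricted model should replace the planned one, or that it would cure differences between sites. Neither is supported. Replacement trades bias against precision, with a standard error factor of up to 2.35 in step 4. If sites within a region differ in positivity and in co-morbidity, positives tested at enrolment at one site are still set against negatives from another. The restricted model recovers the assumed value in steps 1 and 2 by construction.

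Finally, the Figure 1 footnote does not limit tests from the previous 3 days to positive results. Dropping only known positives could itself select on outcome, so any restriction must treat known positives and known negatives alike.

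**Conclusion.** The point holds as a minor to moderate one on a secondary objective. As written, odds ratios for factors related to entry route can be distorted, and a documented recent case can be counted as a negative.

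It does not follow that the odds ratios will be biased. There is no distortion if known positives resemble other positives, and the protocol does not allow size or direction to be derived. The ranges above, 0.90 to 3.72 for an assumed 2.25 and 0.57 to 1.52 for an assumed 1, depend entirely on the chosen shares and frequencies. They are also crude two-by-two values, whereas the planned models are stratified by region. Time since onset is related to route as well, but may truly affect the test result, so a shift in its odds ratio would not by itself show bias.

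The two primary objectives and all follow-up analyses are unaffected.

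**What to change.** - In the summary objectives, section 3.2 and section 4.1, define the groups once and in the same words: by the enrolment test, meaning a test on the enrolment day or within the previous 3 days. State that anyone with an earlier documented positive test is not counted in the negative group.
- In section 4.1, report the model for a positive test twice: in all enrolled, and restricted to participants whose result, positive or negative, was not known before enrolment. In the restricted model, leave out people with an earlier documented positive whatever their re-test shows; keeping only those who re-test positive would again select on outcome.
- Interpret a factor as a determinant of a positive test only if the two models agree, allowing for the wider interval of the restricted one.

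The cost is a few sentences, slightly fewer negatives, and one extra secondary model with lower precision. The loss from removing known positives is smaller when negatives are few, as sections 3.5 and 3.5.3 intend. The date of the qualifying test, and of any earlier positive, must be available for analysis. The entry rules require these dates to be checked, but Appendix B lists only documentation of the test result, so confirm that the case report form records them. Confounding between sites remains and should be acknowledged when the results are reported.

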APPENDIX B: TIME AND EVENTS SCHEDULE

Study Requirement	Enrolment	Follow-up Visits: Day 7, 14 and 28 ^{a)}
Informed consent	X	
Documentation of results of SARS-CoV-2 test	X	
Demographics	X	
Targeted medications	X	
Co-morbidities	X	
Upper respiratory tract swabs ^{b)}	X	
Serum specimen ^{b)}	X	
Health status assessment	X	X
Targeted symptoms	X	X
Dyspnoea severity	X	X
Targetted COVID-19 treatments and medications	X	X
Vital and hospitalization status		X
^{a)} only participants with a positive test for SARS-CoV-2 at enrolment ^{b)} only for participants of the specimen collection sub-study		

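### The logistic models for worsening general health status do not list the enrolment rating as a covariate, so odds ratios for enrolment symptoms and dyspnoea can be attenuated or fall below 1

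*Protocol*

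**What the plan says.** Protocol section 4.1 names the outcomes and the model: "Risk factors for the outcomes (e.g., hospitalization, worsening of general health status) at 7, 14, and 28 days after enrolment will be examined using logistic". A model of that kind makes worsening a yes/no outcome. The risk factors that follow cover demographics, clinical factors, "symptoms and severity of dyspnoea at enrolment", and calendar time. Enrolment health status is not among them.

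In Appendix B the row "Health status assessment" is marked at enrolment and at the day 7, 14 and 28 visits, and nowhere earlier. Section 3.6 has enrolment data include "onset date of symptoms; targeted symptoms, including difficulty breathing", so some participants are already ill when they give the enrolment rating.

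The scale is a set of ordered categories. The objectives in section 3.2 say "Evaluate health status and the percentage reporting excellent or very good health status during follow-up". The number of categories and the lowest one are not given.

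Two other statements bear on the point. Section 4.1 also describes an ordinal outcome built from death, hospitalization and general health status, but does not link it to worsening. Section 3.2 has a separate objective: "Determine the percentage reporting a return to pre-morbid health status during follow-up".

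**The concern.** If worsening means a lower category than at enrolment, its probability depends on where the person started. Someone who rates their health poorly at enrolment tends to move back up (regression to the mean). Someone in the lowest category cannot move down at all unless hospitalization or death counts as worse. Someone in the top category has several steps to fall.

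Enrolment symptoms and dyspnoea plausibly go with a low starting category. In a model without that category, their odds ratios mix two things: what they say about later health, and the mechanical effect of starting low.

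Section 2 reports shortness of breath at presentation as associated with progression. This analysis could show it as weak, null or even protective against worsening, and one objective is to use the data in designing later randomized trials.

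**Working it through.** The protocol gives no figure for this outcome, so there is nothing to reproduce. Tables 1 and 2 concern hospitalization or death only. The check is by simulation, and every numerical input below is an assumption.

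**Set-up A.** There are five categories with cut points −1.2, −0.3, 0.6 and 1.4 on a latent scale where higher is sicker. Dyspnoea (x) is present in 25%.

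- Enrolment score: b = u + 0.8x, with u standard normal.
- Follow-up score: f = 0.5u + s·x − 0.3 + e, with e of SD 0.8.

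Two consequences follow by algebra.

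- Mean change f − b is −0.3 without dyspnoea and −0.3 + (s − 0.8) with it.
- Since u = b − 0.8x, the follow-up mean given the enrolment score is 0.5b + (s − 0.4)x − 0.3. The effect of dyspnoea given starting health is therefore s − 0.4.

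The lowest health category at entry holds 27% of those with dyspnoea and 8% of those without.

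| s | Effect given enrolment score | Mean change, with / without | Worsening OR, unadjusted | Worsening OR, stratified by enrolment category | OR for two lowest categories at follow-up |
|---|---|---|---|---|---|
| 0.4 | 0 | −0.70 / −0.30 | 0.49 | 1.06 | about 2.1 |
| 0.8 | 0.4 | −0.30 / −0.30 | 1.00 | 2.50 | 4.1 |

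For s = 0.4, worsening occurs in 11.8% with and 21.5% without dyspnoea: (0.118/0.882)/(0.215/0.785) = 0.49. The chance of worsening falls from 0.53 in the best starting category to 0 in the lowest. With s = 1.2 the unadjusted OR is 1.86.

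**Which mechanism?** Comparing the unbounded scores f and b directly gives ORs of 0.49 (s = 0.4) and 1.00 (s = 0.8), almost the same as with categories. In set-up A the floor therefore contributes little. The result comes from regression to the mean and from greater average improvement among those with dyspnoea. To isolate the floor, set the slope to 1 (no regression to the mean), keep the 0.3 recovery, and make the dyspnoea deficit the same at both times. The unbounded OR is then 1.0. The category OR is 0.81 with a deficit of 0.8 and noise SD 0.8, and 0.36 with a deficit of 2.0 and noise SD 0.5. A floor alone can distort, strongly only when the entry deficit is large.

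**Set-up B.** There are five levels and dyspnoea in 25%. Dyspnoea shifts enrolment health by 0.5 or 1.0 SD. The enrolment-to-follow-up slope is 0.4 and recovery is 0 or 0.8 SD. Harm is the independent effect of dyspnoea on follow-up health. In the last two columns hospitalization or death is added as a worse state, with odds ratio 2 for dyspnoea. In the first adjusted column those in the lowest category at entry are excluded, because they cannot have the event.

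| Harm (SD) | Unadjusted | Adjusted for enrolment category | Unadjusted, hospitalization/death counted | Adjusted, hospitalization/death counted |
|---|---|---|---|---|
| 0 | 0.40–0.66 | 1.03–1.08 | 0.58–0.95 | 1.15–1.39 |
| 0.3 | 0.63–1.01 | 1.68–1.82 | 0.79–1.31 | 1.78–1.97 |
| 0.6 | 0.92–1.58 | 2.75–3.04 | 1.08–1.80 | 2.82–2.85 |
| 1.0 | 1.42–2.71 | 5.28–6.07 | 1.62–2.77 | 4.86–5.21 |

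The unadjusted value is below the adjusted one throughout. It falls below 1 in some scenarios only.

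**The case against.** The strongest reply has five parts.

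1. **Change and level are different questions.** In set-up A with s = 0.4, people with dyspnoea do improve more on average, so 0.49 describes change correctly. This stands, and the contrast with poor health at follow-up is not by itself a measure of bias. What remains is that the plan seeks risk factors for progression, and an unadjusted change outcome cannot separate a factor's prognostic content from the starting category.

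2. **The reference is not stated.** True: measurement from enrolment is inferred from the schedule. A pre-morbid reference appears in one objective. If worsening were judged against it, and pre-morbid status were unrelated to dyspnoea, set-up A would give an OR of 1.98. But section 4.1 does not tie worsening to pre-morbid status, and Appendix B lists no separate pre-illness assessment.

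3. **The lowest category may still have room.** If worsening includes hospitalization or death, it does. Set-up B shows that this weakens the distortion without removing it.

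4. **This belongs in the statistical analysis plan.** Worsening is given as an example, the risk-factor list is not closed, and section 4.1 defers details. That plan was not available and may settle the matter. The protocol nevertheless already names a change outcome beside predictors of entry severity, so the remark concerns a stated choice.

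5. **Worsening is a legitimate question.** The protocol's synopsis is motivated partly by people who deteriorate after mild presentation. A reader might infer that worsening must be dropped. The documents do not support that, and an unadjusted level at follow-up does not isolate progression either: it gave 1.37 to 2.04 in set-up B with no independent harm.

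**Conclusion.** The point holds in limited form. As section 4.1 and Appendix B read together, the worsening outcome is tied to a starting category that the models do not list. Odds ratios for factors linked to being sicker at entry can be attenuated and, in some scenarios, fall below 1.

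A reader might go further and infer that every such odds ratio is biased to 1 or below, or that dyspnoea will appear protective. Neither follows: with strong harm the unadjusted value stays at 1.42 to 2.71. Nor is lack of room to worsen the main driver in every setting.

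The conclusion rests on the enrolment rating being the reference, on a bounded ordered scale, and on enrolment symptoms tracking enrolment health. The sizes rest on assumed inputs (scale, prevalence, correlations) that the protocol does not give.

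The primary endpoint, its power tables, and the Kaplan-Meier and Cox analyses are untouched. Severity is low to moderate: a nearly free improvement to a secondary analysis.

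**What to change.** In section 4.1 or the statistical analysis plan:

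- State which rating worsening is measured from, and whether hospitalization and death count as worse.
- Include the enrolment health status category as a covariate in the models of general health status.
- Preferably, model the ordinal outcome already named in section 4.1 at days 7, 14 and 28 with that covariate, and also report the model without it, since the two answer different questions.
- Keep worsening, if wanted, as a descriptive summary among participants not in the lowest category at enrolment.

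Appendix B already schedules everything needed, so the cost is wording. The downside is slightly more analysis and an outcome that is less intuitive than worsened or not.
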